## I. Research Objectives and Purpose

- Research Key Questions(s):** Can hypotension prediction index (HPI, ClearSight, Edwards Lifesciences, Irvine, USA) reduce time-to-treatment of epidural labor analgesia (ELA)-associated hypotension?
- Hypotheses:** HPI will have clinically significant reductions in time-to-treatment of ELA-associated hypotension compared to conventional non-invasive blood pressure monitoring methods.

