**e. Protocol specific methods:**

Patients will be screened electronically using the electronic health record upon arrival at the Womancare birth center at UPMC Magee. Patients are eligible if they are pregnant, admitted for labor and delivery, and receiving ELA. If patients are undecided about whether they will receive ELA but are interested in the research, they may be consented and then marked as a "screen failure" if they do not receive ELA. These patients will not be randomized. Patients who receive ELA will be randomized to treatment of hypotension according to conventional monitoring (Group CM) or monitoring by HPI (Group HPI). Randomization will be 1:1 and occurs immediately after informed consent and signature for research activities. Subjects will be informed of their assignment after all research activities and data collection have been completed. Total monitoring time will be 4 hours starting from the initiation of ELA. To enable group comparisons of total time in hypotension, all participants will wear ClearSight and a Conventional Monitoring cuff; Group CM will be blinded to ClearSight output and receive standard care for the treatment of hypotensive events post-epidural-labor analgesia. Group HPI will receive treatment of hypotension according to ClearSight output and specified by the hypotension treatment protocol below.

Clinical research staff who have been trained in ClearSight will apply the device and troubleshoot any problems. Providers will be trained on the monitor, its interpretation, and output, prior to study launch and real time at the time of active study participant enrollment. This training applies only to those participants who will receive non-blinded treatment assignment

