## **ELA Protocol: Combined Spinal Epidural (CSE) Analgesia**

A baseline blood pressure will be recorded immediately prior to the initiation of ELA.

At patient request, an experienced anesthesia provider will perform procedure to place ELA using CSE technique in the sitting position. CSE is chosen due to reliability and rapidity with which hypotension can be predicted within the ELA encounter. A meta-analysis of studies comparing low-dose epidural analgesia with CSE analgesia found no difference in the incidence of hypotension between the two techniques.

The epidural space will be found using loss of resistance to saline. A 25-27g Sprotte needle will be introduced to the subarachnoid space. After confirmation of cerebrospinal fluid (CSF), a spinal dose of 15mcg fentanyl and 2.5mg bupivacaine will be given (this action defines T0 = initiation of CSE). At T0 blood pressure monitoring and data recordings will begin per protocol specified below.

A 19-20g flexible epidural catheter will then be introduced and threaded 5-6cm in the epidural space. Test dose will be delivered through the epidural catheter and will consist of lidocaine 1.5% with epinephrine, 3mL. The anesthesia clinician will declare positive or negative test dose 5 min after administration of test dose. A positive test dose will result in withdrawal from the study.

Maintenance of ELA will be by patient-controlled epidural analgesia using programmed intermittent epidural bolus (PIEB) at our institutional standards: Ropivacaine 0.1% +2mcg/mL fentanyl, 8mL q40min, 8mL demand q8min, maximum hourly volume 24mL. (Smiths CADD®-Solis Infusion System, Infusion Pump, ICU Medical, Dublin, OH). The first PIEB dose is delivered 40 minutes after the initiation of the pump.

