### ***Blood Pressure Monitoring and Hypotension treatment protocol is standardized as below.***

#### **BP MONITORING PROTOCOL**

Group CM	Group HPI
-----------------	------------------

<math>T_0</math> At the time of test dose delivery, automated NIBP cycles will begin q3min for 30 minutes, amounting to a total of at least 10 blood pressure measurements.
 
<math>T_{30}</math> After 30 minutes, NIBP cycles to q15min per existing clinical standards
 
<math>T_{4\text{hours}}</math> Monitoring for research ends
	
<math>T_0</math> At the time of test dose delivery, Clearsight monitoring continues.
 
<math>T_0 - T_{4\text{hours}}</math> ClearSight monitoring is continuous
 
<math>T_{4\text{hours}}</math> Monitoring for research ends

--	--

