### \*\*Hypotension as defined above

**Key:** **MAP:** mean arterial pressure; **CM:** conventional monitoring (standard care); **HPI:** hypotensive prediction index group (ClearSight device and algorithm); **BP:** blood pressure; **SBP:** systolic blood pressure; **NIBP:** non-invasive blood pressure; **IVP:** Intravenous push

e. **Electronic Health Record Variables Collected:**

- Age
- Race/Ethnicity
- Insurance status
- Gravidity
- Parity
- Estimated gestational age
- Body mass index
- Induction vs Spontaneous Labor
- Last known cervical exam at the time of ELA initiation
- Pain score immediately prior to ELA initiation
- Total vasopressor doses from time of ELA initiation until delivery
- Time of hypotensive event start to time of treatment for hypotension
- Changes in fetal heart rate Yes/No
  - If Yes: Time, in minutes, from ELA initiation until category change detected
- Presence or absence of fetal heart rate decelerations within 1 hour of initiation of ELA (yes/no)
- Mode of delivery
- Neonatal weight
- Neonatal Apgar scores
- Neonatal cord blood pH

3. **Risks/Benefits:**

Benefits

Close monitoring and treatment of hypotension

Risks

Loss of confidentiality

Discomfort with devices

Inconvenience answering questions

Risk of obtaining a false positive reading and being given fluids or other management of blood pressure that was not necessary.

4. **Data Analysis:**

a. **Data collection form:** See Appendix

b. **Statistical Analysis Plan**

Descriptive statistics will be calculated for variables and compared between groups. We will report mean  $\pm$  SD for normally distributed continuous data; median (interquartile range) for data not normally distributed or for data with outliers or ordinal data; and number (percentage) for categorical data. Kolmogorov–Smirnov test will be applied to test for normality of data distribution. An unpaired two-tailed t test will be used for comparing parametric data between groups, and Mann–Whitney U and Wilcoxon rank sum tests will be used for nonparametric data. The chi-square test or Fisher exact test will be applied as appropriate for comparing proportions between groups.  $P < 0.05$  will be considered statistically significant.

*Primary Outcome Analysis (Survival Analysis)*

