### ***Secondary Outcome Analyses***

The secondary outcomes that will be compared between groups will include total time in hypotension, nausea, vomiting, total phenylephrine and ephedrine (mg) doses, total intravenous fluids in labor (mL), changes in fetal heart rate category, presence, or absence of fetal rate decelerations within one hour of initiation of ELA, and hemodynamic variables (CO, CI, SV, SVV). We will report mean  $\pm$  SD for normally distributed continuous data; median (interquartile range) for data not normally distributed or for data with outliers or ordinal data; and number (percentage) for categorical data. Kolmogorov–Smirnov test will be applied to test for normality of data distribution. An unpaired two-tailed t test will be used for comparing parametric data between groups, and Mann–Whitney U and Wilcoxon rank sum tests will be used for nonparametric data. The chi-square test or Fisher exact test will be applied as appropriate for comparing proportions between groups.  $P < 0.05$  will be considered statistically significant.

In Group HPI, we will use mediation and moderation analyses to assess the ELA  $\rightarrow$  Hypotension association explained by hemodynamic parameters: Cardiac Output (CO), Stroke Volume (SV), Stroke Volume Variation (SVV), Systemic Vascular Resistance (SVR).

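### The 4-hour hypotension outcomes have no cutoff at delivery, operative anesthesia or a repeat block, and the vasopressor and fluid totals use a different window

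*Combined protocol and SAP*

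**What the plan says.** The hypothesis in section I is that "HPI will have clinically significant reductions in time-to-treatment of ELA-associated hypotension compared to conventional non-invasive blood pressure monitoring methods". Time-to-treatment is one of the primary outcomes (III.2.c), and total time with MAP below 65 mmHg is an exploratory secondary outcome.

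The observation period is set in Protocol specific methods (III.2.e): "Total monitoring time will be 4 hours starting from the initiation of ELA". The BP Monitoring Protocol table repeats this for both groups. At 4 hours, "Monitoring for research ends", and no other end is given. The start is the spinal dose ("this action defines T0 = initiation of CSE"), although the same table places T0 at the test dose. That difference is small for the present point.

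The list of electronic health record variables uses other windows. Time-to-treatment is "Time of hypotensive event start to time of treatment for hypotension", with no link to delivery or to the state of the block. Vasopressors are "Total vasopressor doses from time of ELA initiation until delivery". Secondary Outcome Analyses describes intravenous fluids as those given in labor, while the outcome list in III.2.c gives fluids no window. "Mode of delivery" is collected, but no analysis uses it, and the list does not include the time of delivery.

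The Primary Outcome Analysis fits proportional hazards models to treatment-free time and states no censoring rule.

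**The concern.** A woman can stop being a patient under labor analgesia before 4 hours have passed. She may deliver, receive anesthesia for a cesarean, or have a failed catheter replaced with a new neuraxial dose. A fall in pressure after that point may come from the new block or from the delivery, not from the analgesia under study. A flat 4-hour window with no cutoff keeps such episodes in time-to-treatment and in minutes below 65 mmHg.

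A survival model also needs a defined end of follow-up. For a woman who delivers at hour 2, an analyst could censor at delivery, follow her to hour 4, or drop her under the incomplete-data criterion. The plan does not choose. Dropping her would be an exclusion after randomization that depends on the course of labor.

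The stake is the number that the pilot passes on. III.2.a says the sample is too small to show a difference but should give an estimate for continuing the study. With about six events, that estimate is sensitive to a single misattributed one.

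**Working it through.** **1. Is there a cutoff anywhere?** These are the places where one could stand:

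- Criteria (III.2.d): the entries that could act after the block is started are unintentional dural puncture at placement, inability to use the device, and incomplete data. None mentions delivery, cesarean or block replacement.
- ELA Protocol: a positive test dose leads to withdrawal.
- BP Monitoring Protocol table: the 4-hour end only.
- Hypotension Treatment Protocol table: no end point.
- Survival analysis: no censoring rule.

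So there is none for time-to-treatment or for time in hypotension.

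**2. Do the windows agree?**

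| Quantity | Window in the documents |
|---|---|
| Time-to-treatment, time with MAP below 65 mmHg | 4 hours from ELA initiation |
| Vasopressor totals | ELA initiation to delivery |
| Intravenous fluids | In labor (analysis text); none given (outcome list) |
| Fetal heart rate decelerations | 1 hour from ELA initiation |

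In a long labor the vasopressor total runs past the monitored 4 hours. In a short one it stops earlier. In a cesarean it includes doses given for the operative anesthetic before birth. The decelerations have their own short window and are less exposed.

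**3. The plan's own event count.** Section III.2.b gives N = 30 and 20%, so 30 × 0.20 = 6. This reproduces. With 1:1 allocation and equal incidence that is 6 / 2 = 3 per group. One extra event in one group makes 4 against 3, a crude ratio of 1.33 where there is no difference, and 1 / (6 + 1) = 14% of all events.

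**4. Events that could be added.** The documents give no rate for these transitions, so two assumptions are needed:

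- f: share of patients with a transition within 4 hours, 5–30%
- q: chance of a first treated episode after it, among women not already treated, 10–60%

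A woman treated earlier adds no new first event, hence the factor 1 − 0.20 = 0.80.

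Added first events = 30 × f × 0.80 × q; share = added / (6 + added).

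| f | q = 10% | q = 30% | q = 60% |
|---|---|---|---|
| 5% | 0.12 (2%) | 0.36 (6%) | 0.72 (11%) |
| 10% | 0.24 (4%) | 0.72 (11%) | 1.44 (19%) |
| 20% | 0.48 (7%) | 1.44 (19%) | 2.88 (32%) |
| 30% | 0.72 (11%) | 2.16 (26%) | 4.32 (42%) |

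**5. What a cutoff would cost.** Assume a constant hazard that gives 20% at 4 hours: h = −ln(0.80) / 4 = 0.0558 per hour. With a share f censored at t hours, expected ELA events = 30 × [(1 − f) × 0.20 + f × (1 − exp(−h t))].

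- f = 5%, t = 3: 30 × (0.190 + 0.05 × 0.154) = 5.9 events; 30 × 0.05 × 1 = 1.5 of 120 patient-hours removed.
- f = 30%, t = 2: 30 × (0.140 + 0.30 × 0.106) = 5.2 events; 30 × 0.30 × 2 = 18 of 120 patient-hours removed.

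If hypotension clusters soon after the spinal dose, the loss of events is smaller.

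**The case against.** The strongest reply is that a monitoring duration is not an attribution rule. The objective is limited to ELA-associated hypotension, and no sentence says that hypotension under surgical anesthesia counts. That is right: the inclusion is inferred from silence. But the model needs an end of follow-up, and the only one stated is 4 hours.

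Some stronger readings are tempting, and the documents do not support them.

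- *Vasopressors given after delivery are counted.* They are not: that total stops at delivery. What remains is the mismatch with the 4-hour window and the doses given before birth at a cesarean or after a replaced block.
- *A positive test dose is the only exit after the block.* The criteria also list dural puncture, inability to use the device and incomplete data. The last two are loose enough that someone might apply them to a woman who delivers early, which is a reason to settle the matter in advance.
- *The events could never be separated afterwards.* The data collection form is not in the available text, and a vasopressor total up to delivery implies that delivery time is known. Only the printed variable list can be judged.
- *A definite share of events is contaminated.* No transition rate is given. The internal figure of 20–30% treated with a vasopressor within 4 hours is not said to exclude operative cases, so some of these events may already lie within the 6. A preventive dose is also not in itself an episode of MAP below 65 mmHg.

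It is also fair that ease of use and feasibility, listed first among the primary outcomes, are barely affected, and that the secondary outcomes are exploratory.

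**Conclusion.** The point holds for two outcomes, time-to-treatment and time with MAP below 65 mmHg: a fixed 4-hour window with no cutoff when labor analgesia ends. It holds separately for the vasopressor and fluid totals, whose windows do not match the monitored period.

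The size cannot be fixed from the documents. Over the assumed ranges, 0.1 to 4.3 first events are added to the 6 expected, or 2% to 42% of those counted. A middle case (f = 10%, q = 30%) gives 0.7 events, or 11%. These figures treat the 6 as all ELA-related; if operative cases are already inside the 20%, part of the contamination is within the 6 and not on top of it. The documents do not show which group would be favored. The conclusion does not need the upper end of the range, since one event is enough to move an estimate built on about three per group. This should be corrected before the pilot estimate is used to plan a larger trial.

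**What to change.** Change analysis and data capture only; clinical care stays as it is.

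1. End each patient's outcome window at the earliest of 4 hours, delivery, first dose given for operative anesthesia, or a repeat neuraxial procedure.
2. Censor time-to-treatment at that point, and report time in hypotension over the time actually observed.
3. Align the vasopressor and fluid totals to the same window.
4. Add the clock time and the reason for the end of the window to the health record variable list.
5. State that women who reach the cutoff early stay in the analysis and are not removed as having incomplete data. Keep collecting delivery and neonatal outcomes on everyone.

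The cost is a short protocol paragraph, one clock time and one reason per patient, and slightly less observed time. There is one real statistical downside. Fetal heart rate concerns prompt blood pressure treatment under the existing clinical standards and may also lead to cesarean, so censoring there may be informative. Report the number and reason for early cutoffs by group, and show the full 4-hour analysis as a sensitivity analysis.

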***Pre-ELA Protocol***

Participants will receive 500mL crystalloid co-load to be started and administered during placement of ELA. Because pregnant women in lateral decubitus positions can result in 10mmHg differences in dependent and upper arm blood pressures, the anticipated initial post-ELA decubitus position of the patient will be clarified as Right or Left lateral decubitus; standard monitoring will be applied including pulse oximeter and non-invasive blood pressure (NIBP) cuff affixed over the patient's arm anticipated to be in the upper (not dependent) position. In Group HPI both ClearSight and NIBP monitors will be applied on the same arm.

## **ELA Protocol: Combined Spinal Epidural (CSE) Analgesia**

A baseline blood pressure will be recorded immediately prior to the initiation of ELA.

At patient request, an experienced anesthesia provider will perform procedure to place ELA using CSE technique in the sitting position. CSE is chosen due to reliability and rapidity with which hypotension can be predicted within the ELA encounter. A meta-analysis of studies comparing low-dose epidural analgesia with CSE analgesia found no difference in the incidence of hypotension between the two techniques.

The epidural space will be found using loss of resistance to saline. A 25-27g Sprotte needle will be introduced to the subarachnoid space. After confirmation of cerebrospinal fluid (CSF), a spinal dose of 15mcg fentanyl and 2.5mg bupivacaine will be given (this action defines T0 = initiation of CSE). At T0 blood pressure monitoring and data recordings will begin per protocol specified below.

A 19-20g flexible epidural catheter will then be introduced and threaded 5-6cm in the epidural space. Test dose will be delivered through the epidural catheter and will consist of lidocaine 1.5% with epinephrine, 3mL. The anesthesia clinician will declare positive or negative test dose 5 min after administration of test dose. A positive test dose will result in withdrawal from the study.

Maintenance of ELA will be by patient-controlled epidural analgesia using programmed intermittent epidural bolus (PIEB) at our institutional standards: Ropivacaine 0.1% +2mcg/mL fentanyl, 8mL q40min, 8mL demand q8min, maximum hourly volume 24mL. (Smiths CADD®-Solis Infusion System, Infusion Pump, ICU Medical, Dublin, OH). The first PIEB dose is delivered 40 minutes after the initiation of the pump.

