## III. Investigational Plan

### 1. **Study design:** Prospective randomized controlled trial

### 2. **Methods:**

a. **Size of study groups(s):** The primary outcomes are 1.) ease and feasibility of use of the ClearSight monitoring system during labor and delivery, post-epidural-labor analgesia placement; and 2.) time-to-treatment of hypotension, defined as MAP <65 mmHg for more than 1 minute. Our initial pilot sample is expected to identify the ability to use the ClearSight monitoring in the labor and delivery suite, the patient adherence to the finger cuff monitors, and the feasibility of hypotension detection at the central monitors. The pilot sample (N = 30) is not expected to demonstrate significant differences in the relation between mode of blood pressure measurement and time-to-treatment of hypotension but should yield an estimate of the potential differences for a continuance of study.

b. **Environment and Estimated timeline to sample size acquisition:** UPMC Magee performs about 7,400 ELA annually, a range of 20-30 ELA daily. Based on a meta-analysis of trials, the estimated incidence of hypotension after initiation of neuraxial analgesia during labor is approximately 19% (range: 3-35%). Our internal data that shows approximately 20-30% of patients receiving ELA require treatment with a vasopressor within the first 4 hours of ELA initiation; we will use the conservative estimate of 20%. Our internal experience with similar trials also informs our timeline: in our prior experiences with similar labor and delivery trials we have achieved a consistent approach-to-recruit ratio of about 25%. Based on our volume, ELA utilization, eligibility criteria, and rates of ELA-associated hypotension, we estimate a total of 5-8 weeks of recruitment. A total of N=30 patients will be enrolled with a predicted 20% (n=6) experiencing hypotension events of interest.

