### c. **Outcomes:**

Primary outcome:

Ease of use of ClearSight blood pressure monitoring system

(0 – 10) Ratings from patient and patients' assigned nurse during ELA

Feasibility of blood pressure monitoring (yes/no response from assigned nurse regarding patient care.

Time-to-treatment of hypotension (minutes)

Secondary outcomes: (only exploratory)

Total time in hypotension with MAP <65 mmHg

Nausea

Vomiting

Total phenylephrine, mg

Total ephedrine, mg

Total intravenous fluids, mL  
Changes in fetal heart rate category  
Presence or absence of fetal heart rate decelerations within 1 hour of initiation of ELA  
CO, CI, SV, SVV

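### The pre-ELA blood pressure enters no named analysis and no pre-block ClearSight baseline is specified, so exploratory haemodynamic comparisons at about 15 per arm give up precision that baseline adjustment could recover

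*Combined protocol and SAP*

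**What the plan says.** **Baseline reading.** The ELA Protocol section has a blood pressure taken just before the procedure: "A baseline blood pressure will be recorded immediately prior to the initiation of ELA".

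**Start of recording.** The same section defines T0 as the spinal dose and adds: "At T0 blood pressure monitoring and data recordings will begin per protocol specified below". The BP Monitoring Protocol table ties T0 to delivery of the epidural test dose instead, and for Group HPI describes ClearSight as already under way at that moment. Under Protocol specific methods, every participant wears ClearSight. The Pre-ELA Protocol describes putting it on beforehand for Group HPI only; no section says when it goes on in Group CM.

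**Analysis.** Secondary Outcome Analyses lists total time in hypotension and CO, CI, SV and SVV among the outcomes. For continuous data the plan is: "An unpaired two-tailed t test will be used for comparing parametric data between groups", with rank tests when the data are not normal. No baseline term appears. The Outcomes section marks the secondary outcomes as exploratory only.

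**Size.** "A total of N=30 patients will be enrolled with a predicted 20% (n=6) experiencing hypotension events of interest". Allocation is 1:1.

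**The concern.** CO and SV can be expected to vary between patients before any block is given, and time spent below a fixed 65 mmHg line depends partly on where a patient's MAP started. An unadjusted comparison leaves that variation in the error term. With about 15 per arm the groups can also start some distance apart by chance.

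The pilot's stated purpose is to estimate potential differences for a continuation study, so the width of its intervals matters even though it is not powered. An unadjusted standard deviation carried forward would also make the next trial larger than an adjusted design needs.

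Timing makes this more than a matter of analysis choice. A test can be changed before the data are examined, but haemodynamic values that were never recorded before the block cannot be recovered.

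**Working it through.** **The plan's own figure.** 0.20 × 30 = 6 patients with hypotension, as stated. At 1:1 that is 15 per arm and about 3 hypotensive patients per arm. The documents give no power calculation, no SD and no baseline-outcome correlation. The correlations (r) and SDs below are therefore assumptions, shown over a range.

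**1. Chance imbalance at baseline.** The SD of the difference in arm means is √(2/15) = 0.365 patient SDs. With an assumed between-patient MAP SD of 10 mmHg this is 3.65 mmHg, and the chance that the arms start more than 5 mmHg apart is 2 × (1 − Φ(5/3.65)) = 17%. At SD 8 it is 9%; at SD 12 it is 25%. Only the fraction set by the baseline-outcome slope reaches the outcome: at r = 0.5, an imbalance of 0.365 SD shifts the outcome difference by 0.5 × 0.365 = 0.18 SD.

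**2. Continuous haemodynamic outcomes.** The unadjusted 95% half-width is t(0.975; 28 df) × √(2/15) = 2.048 × 0.365 = 0.75 SD. For ANCOVA on a baseline of the same measure, residual variance is (1 − r²) × 27/26, where 27/26 is the cost of estimating one covariate with N = 30, and there are 27 df (t = 2.052). Equivalent n per arm is 15 divided by that variance.

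| Assumed r | Residual variance | Half-width (SD) | Change in width | Equivalent n per arm |
|---|---|---|---|---|
| 0 | 1.04 | 0.76 | +2% | 14.4 |
| 0.3 | 0.945 | 0.73 | −3% | 15.9 |
| 0.5 | 0.779 | 0.66 | −12% | 19.3 |
| 0.7 | 0.530 | 0.55 | −27% | 28.3 |

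Simulated trials at 15 per arm gave the same width ratios: 1.02, 0.97, 0.88 and 0.73. The difference detectable with 80% power (two-sided 0.05) is 1.06 SD unadjusted, and 1.03, 0.94 and 0.77 SD at r = 0.3, 0.5 and 0.7.

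**3. Time with MAP below 65 mmHg.** At 20% incidence about 80% of patients have zero time. I modelled time as the depth by which a normal latent value falls below its 20th percentile. Latent r of 0.3, 0.5 and 0.7 then leaves R² of only 0.04, 0.11 and 0.21 between baseline and time. Simulated trials at 15 per arm showed mean interval width falling by about 0%, 4% and 10–11%.

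**4. Where recording starts.** The ELA Protocol section starts data recording at T0, the spinal dose. The monitoring table has ClearSight already running at T0 in Group HPI and places T0 at the test dose, which the ELA Protocol section puts after the spinal dose. Read together, they do not settle whether any pre-block ClearSight data are kept, and neither specifies a pre-block value for analysis.

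**The case against.** **Baseline pressure has uses elsewhere.** A reader might infer that it is never used, or not collected. The documents do not support that. The Hypotensive Event Measurement section keeps a clinical trigger defined by a fall in systolic pressure from baseline. The proportional hazards model screens covariates without naming them, so baseline pressure is not excluded there. Its absence from the Electronic Health Record Variables list shows little, because that list also omits CO, nausea and the ease-of-use ratings. The data collection form is assigned to an appendix whose contents are not in the text reviewed.

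**Recording may begin earlier than T0.** Reading the plan as starting ClearSight recording only at T0 treats one side of an internal conflict as settled. What stands is that no pre-T0 value is specified.

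**Adjustment is not entirely free.** If recording does start at T0, there is no CO or SV baseline to adjust for. A pre-block reading would be taken during sitting placement with the fluid co-load running, while later readings are expected in lateral decubitus, so the correlation may be low. This objection stands, and it is why the range runs down to r = 0.

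**The stakes are modest.** The outcomes are exploratory, and the plan says of the pilot that it "is not expected to demonstrate significant differences in the relation between mode of blood pressure measurement and time-to-treatment of hypotension". The unadjusted interval already allows for chance imbalance. This too stands: it limits the importance of the point but does not remove it.

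**Conclusion.** The point holds as a precision improvement. The secondary comparisons are unadjusted, the recorded baseline pressure enters no named analysis, and no pre-block ClearSight baseline is specified in either group. For CO, CI, SV and SVV the effect of adjustment runs from an interval 2% wider (r = 0) to one 27% narrower (r = 0.7), on correlations the documents do not give.

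Two stronger readings should be resisted. One is that chance imbalance biases the comparisons: it does not under randomisation. The other is that the 12% and 27% gains apply to time in hypotension: with about 80% zeros the narrowing there is about 0% to 11%, and essentially nil at a latent correlation of 0.3.

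**What to change.** - Reconcile the ELA Protocol section with the BP Monitoring Protocol table on which action defines T0 and on when ClearSight recording begins.
- Apply ClearSight and start recording before the spinal dose in both groups, with Group CM's output still blinded. Store a short pre-block mean of MAP, CO, CI, SV and SVV, and state the averaging window and the patient's position.
- In Secondary Outcome Analyses, replace the unpaired tests for CO, CI, SV and SVV by ANCOVA on the pre-block value of the same variable.
- For time with MAP below 65 mmHg, pre-specify baseline MAP as the single covariate, with permutation or robust inference because plain linear ANCOVA suits so many zeros poorly.

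Cost: a few sentences, a few minutes of extra recording per patient and one degree of freedom (28 to 27). If the seated baseline proves uninformative, the loss is an interval about 2% wider.
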